9 DISPOSITION AND WITHDRAWALS

All participants who provide informed consent will be accounted for in this study.

9.1 DISPOSITION

Disposition of participants will be summarized for the Enrolled Analysis Set. The number of participants in each analysis set (ENR, ITT and SAF) will be summarized by count and percentage over cohorts 1-4 pooled. Percentages will use the ENR analysis set as the denominator. Reasons for exclusion for each analysis set will be presented in a listing.

The number and percentage of screen failure participants using the ENR analysis set as the denominator will be presented. The number of individuals who fail to meet the individual inclusion criteria and/or meet the individual exclusion criteria will be presented using the number of screen fail participants as the denominator. A participant will be counted across multiple criteria if satisfied.

Count and percentage of study/treatment completers will be summarized along with non-completers. For non-completers the reason for discontinuation from study/treatment will also be

Document: \\ieedc

 $vnasc01\\BIOSdata\\Sanofi\\Fabrazyme\\IAB16602\\Biostatistics\\Documentation\\SAP\\SAP\\Sanofi\\Finally and the properties of th$

Version\lps17726-16-1-9-sap.docx

Author: Version Number: Final V1.0

Version Date: 22Oct2024

Template No.: CS_TP_BS016 Revision 7 Reference: CS_WI_BS005

Effective Date: 01Nov2021

PROTOCOL LPS17726

Analysis Plan Template

Page 36 of 65

summarized. All reasons, including additional comments will be presented in a listing.

Disposition information is recorded in the following eCRF pages:

- End of Study Treatment
- End of Study

9.2 PROTOCOL DEVIATIONS

Protocol Deviations (PDs) identified will recorded in the IQVIA Clinical Trial Management System (CTMS) by IQVIA Clinical, as per the Protocol Deviation Management Plan.

Protocol Deviations (PDs) will be reviewed by the cross functional teams in Sanofi and IQVIA on a regular basis throughout the study.

9.2.1 Protocol Deviation Severity Classifications

- Critical Protocol Deviation: A deviation from Protocol-related procedures that threatens integrity of data, adversely affects participants and/or could invalidate acceptability of a project (or part of it).
- **Major Protocol Deviation:** A deviation from Protocol-related procedures that could affect integrity of the data or adversely affect participants.
- **Minor Protocol Deviation:** A deviation from Protocol-related procedures that will not adversely affect participants or data integrity.

9.2.2 Analysis of Protocol Deviations

The total number and percentage of participants who record at least one major or critical protocol deviation in the study per classification and category will be provided for cohorts 1-4 pooled for the ITT analysis set. A participant can be counted over several classifications but only once per category. A corresponding listing of all major or critical protocol deviations will be provided per cohort for the ITT analysis set.

Document: \\ieedc

vnasc01\BIOSdata\Sanofi\Fabrazyme\IAB16602\Biostatistics\Documentation\SAP\SAP\Sanofi\Final

Version\lps17726-16-1-9-sap.docx

Author: Version Number: Final V1.0

Version Date: 22Oct2024

Template No.: CS_TP_BS016 Revision 7 Reference: CS_WI_BS005

Effective Date: 01Nov2021

PROTOCOL LPS17726

Analysis Plan Template

Page 37 of 65

Deviations will be presented if the frequency is greater than 0, according to the following categories as per the PD management plan:

- Informed Consent and Process
- Inclusion Criteria
- Exclusion criteria
- Laboratory Assessment
- Study Procedures
- Safety
- Randomization
- Visit Schedule
- IP conditions
- IP preparation
- IP administration
- Administrative
- Training/Delegation non-compliance
- PI oversight
- PI & site staff qualification
- Source documents
- Communication with IRB
- Investigator site file
- Adequate site staff and backup
- Site processes/Site systems
- Safety letters management
- Facilities/Equipment
- Other

Document: \\ieedc

 $vnasc01 \\ \label{losdata} Sanofi\\ \label{losdata} Sa$

Version\lps17726-16-1-9-sap.docx

Author: Version Number: Final V1.0

Version Date: 22Oct2024

Template No.: CS_TP_BS016 Revision 7 Reference: CS_WI_BS005

Effective Date: 01Nov2021

Page 38 of 65

10 DEMOGRAPHIC AND BASELINE CHARACTERISTICS

Demographic data and baseline characteristics are recorded in the following eCRF pages: Demography, Pregnancy test, Pre-study Fabrazyme Treatment and Vital Signs.

Demographic data and baseline characteristics will be presented for the ITT analysis set.

The following demographic and baseline characteristics will be reported for this study:

- Age (years)
- Age group (Children 2-10 years, Adolescents 11-17 years, Adults 18-65 years)
- Sex (Male, Female, Unknown)
- Ethnic origin (American Indian or Alaska Native, Asian, Black or African American, Native Hawaiian or Other Pacific Islander, White, Not Reported, Unknown)
- Hispanic Ethnicity (Hispanic or Latino, Not Hispanic or Latino, Not Reported, Unknown)
- Women of child-bearing potential (Yes, No with reason, Unknown)
- Baseline Weight (kg)
- Baseline Weight by Category (≥30 kg, <30 kg)
- Pre-study Fabrazyme infusions (dose and duration)
- Duration of Fabrazyme treatment pre-study (full months)

Unknown corresponds to either the selection on the CRF or for missing data.

A summary table for cohorts 1-4 pooled will be provided. A corresponding listing per cohort will be provided for all characteristics, where the pre-study Fabrazyme duration and dose will present all records as collected on the eCRF.

Document: \\ieedc-

Author:

vnasc01\BIOSdata\Sanofi\Fabrazyme\IAB16602\Biostatistics\Documentation\SAP\SAP\Sanofi\Final

Version\lps17726-16-1-9-sap.docx

Version Number: Final V1.0

Version Date: 22Oct2024

Template No.: CS_TP_BS016 Revision 7 Reference: CS_WI_BS005

Effective Date: 01Nov2021

PROTOCOL LPS17726

Analysis Plan Template

Page 39 of 65

11 MEDICAL HISTORY

Medical History conditions are defined as those conditions which stop prior to or at Screening.

Medical History data is captured on the following eCRF page: Current or Medical History Condition where Ongoing is not indicated.

Medical History information will be coded using Medical Dictionary for Regulatory Activities (MedDRA) version 27.0 or higher depending on the version in effect at IQVIA at time of database lock.

Medical History will be presented for the ITT analysis set and summarized by System Organ Class (SOC) and Preferred Term (PT) for cohorts 1-4 pooled.

There will also be a listing per cohort detailing the SOC, PT, Reported Name per record, along with the corresponding start and end dates recorded.

12 CURRENT MEDICAL CONDITIONS

Current medical conditions are conditions other than the indication being studied which started prior to or at Screening and are ongoing at the date of Screening.

Current medical conditions are captured in the following eCRF page: Current or Medical History Condition where Ongoing is indicated.

Current medical conditions will be coded using Medical Dictionary for Regulatory Activities (MedDRA) version 27.0 or higher depending on the version in effect at IQVIA at time of database lock.

Current medical conditions will be presented for the ITT analysis set and summarized by System Organ Class (SOC) and Preferred Term (PT) for cohorts 1-4 pooled.

Document: \\ieedc

vnasc01\BIOSdata\Sanofi\Fabrazyme\IAB16602\Biostatistics\Documentation\SAP\SAP\Sanofi\Final

Version\lps17726-16-1-9-sap.docx

Author: Version Number: Final V1.0

Version Date: 22Oct2024

Template No.: CS_TP_BS016 Revision 7 Reference: CS_WI_BS005

Effective Date: 01Nov2021

PROTOCOL LPS17726

Analysis Plan Template

Page 40 of 65

There will also be a listing per cohort detailing the SOC, PT, Reported Name per record, along with the corresponding start and end dates recorded.

13 MEDICATIONS

Non investigational prior, concomitant, and post-treatment medications are captured on the following eCRF page: Concomitant Medications Review.

Pre and rescue medications provided on the protocol are captured on the eCRF page: Pre-Medications and Rescue Medications. In the case a participant is administered an alternative pre or rescue medication to those outlined in the protocol such medications will be captured in the Concomitant Medications Review eCRF page.

All medications will be coded using World Health Organization (WHO) Drug Global dictionary, version B3 March 2023 or higher depending on the version in effect at IQVIA at time of database lock.

13.1 PRIOR, CONCOMITANT AND POST-TREATMENT MEDICATIONS

See Section 20.2, for handling partial dates for medications.

- Prior medications are those which start prior to the first dose of Fabrazyme, regardless of stop date.
- Concomitant medications are those received by the participant concomitantly to Fabrazyme during the study treatment period. The start date of these medications can either be prior to, on or after the first dose of Fabrazyme but not after the date of the last Fabrazyme infusion in the study treatment period. The end date of these medications must be after the first dose of Fabrazyme in the study treatment period or missing (ongoing).
- Post-treatment medications are those which are taken after the last dose of

Document: \\ieedc

vnasc01\BIOSdata\Sanofi\Fabrazyme\IAB16602\Biostatistics\Documentation\SAP\SAP\Sanofi\Final

Version\lps17726-16-1-9-sap.docx

Author: Version Number: Final V1.0

Version Date: 22Oct2024

Template No.: CS_TP_BS016 Revision 7 Reference: CS_WI_BS005

Effective Date: 01Nov2021

PROTOCOL LPS17726

Analysis Plan Template

Page 41 of 65

Fabrazyme in the study treatment period, up to the end of the study, including those with a missing end date (ongoing).

A medication can be classified as a combination of prior, concomitant, and post-treatment if any of the above are satisfied, ie, a medication can be prior, concomitant and post-treatment if the start date is prior to the first dose of Fabrazyme and continues to be taken after the last dose of Fabrazyme (ongoing or stop date is after last dose of Fabrazyme).

If the classification cannot be determined the medication will be considered as prior, concomitant, and post-treatment.

13.2 PRE AND RESCUE MEDICATIONS

All participants will receive acetaminophen and one antihistamine as non-investigational prophylactic premedication, 30 minutes prior to each infusion. In case of IAR occurrence, the participant will receive dexamethasone and montelukast as rescue medication, and both drugs will be given from this time forward as prophylactic premedication, together with acetaminophen and the antihistamine, 30 minutes prior to all further infusions. The interventions are presented in tables 3 and 4 in the protocol.

13.3 ANALYSIS OF MEDICATIONS

Medications will be summarized for the ITT analysis set, by number and percentage of participants in cohorts 1-4 pooled according to Anatomical Class (ATC) drug class (level 1) and Anatomical Therapeutic Class (ATC) drug class (level 3). A medication can be counted over several level 1 categories. In summary outputs multiple medication usage by a participant in the same level 3 category will be counted only once in that category. All medications will be provided in listings per cohort for the ITT analysis set and will include the start and end dates of the medication (if known), reason(s) for why the medication was given, dosage, frequency and route. Medications presented in listings will be coded by Anatomical Class (ATC) drug class (level 1), Therapeutic Class (ATC) drug class (level 3) and preferred name.

Document: \\ieedo

Author:

vnasc01\BIOSdata\Sanofi\Fabrazyme\IAB16602\Biostatistics\Documentation\SAP\SAP\Sanofi\Final

Version\lps17726-16-1-9-sap.docx

Version Number: Final V1.0

Version Date: 22Oct2024

Template No.: CS_TP_BS016 Revision 7 Reference: CS_WI_BS005

Effective Date: 01Nov2021

PROTOCOL LPS17726

Analysis Plan Template

Page 42 of 65

14 STUDY MEDICATION COMPLIANCE

Compliance is based on the accumulation of the planned and actual dose (mg/kg) inputs on the Fabrazyme eCRF pages at each visit and is derived and analyzed in accordance with Sections 14.1 and 14.2.

14.1 DERIVATIONS

For each participant, compliance to Fabrazyme is defined as the percentage of the sum of actual dose versus sum of planned dose:

• Compliance (%) = [Sum of Actual dose received (mg/kg) / Sum of Planned dose (mg/kg)]* 100

If actual dose received (mg/kg) is missing for at least one visit, then overall compliance (%) will be missing and categorized as not assessable.

14.2 ANALYSIS OF COMPLIANCE

Compliance will be summarized for cohorts 1-4 pooled as described in Section 7: 'Statistical Considerations' for the SAF analysis set. The count and percentage of participants in the following categories will also be reported:

- <80%
- 80-100%
- >100%
- Not Assessable

A listing by cohort presenting compliance (%) and group will be provided for the SAF. The listing will also include the planned and actual doses (mg/kg) recorded at each visit per participant.

Document: \\ieedc-

[figure not shown]
Version\lps17726-16-1-9-sap.docx

Author: Version Number: Final V1.0

Version Date: 22Oct2024

Template No.: CS_TP_BS016 Revision 7 Reference: CS_WI_BS005

Effective Date: 01Nov2021

Page 43 of 65

15 ENDPOINT EVALUATION

15.1 PRIMARY ENDPOINTS

15.1.1 PRIMARY ENDPOINT VARIABLE(S)

15.1.1.1 SHORTEST INFUSION DURATION EACH PARTICIPANT TOLERATES

The shortest infusion duration tolerated is the actual shortest duration (highest infusion rate) of a completed infusion tolerated by the participant without experiencing a second IAR.

A completed infusion is an infusion during which the entire amount of the study drug planned to be given at the visit has been delivered to the participant via infusion and the question "Was the infusion adjusted from the planned infusion?" is answered either "Infusion not changed" or "Infusion interrupted" on the Fabrazyme eCRF page. If the infusion was interrupted, it will only be considered completed if it was restarted, ie, the stop time of study drug infusion is later than the stop time of infusion interrupted.

An infusion is considered tolerated if it is completed within an actual duration (excluding any interruptions) not exceeding 120% of planned duration, without IAR. If the participant receives several infusions at the same planned duration during the study treatment period, the infusion duration will be considered tolerated if the last infusion with the duration is tolerated. Data for infusion duration tolerated at each visit (scheduled and unscheduled) is captured on the Fabrazyme eCRF pages.

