4.0 STUDY DESIGN

4.1 Overall Design

This is a Phase 4, prospective, open label, single arm, interventional study, to be conducted in the US, to evaluate the safety and tolerability of Fabrazyme at approved dose of 1 mg/kg with increases in the infusion rate and reduced infusion volume.

Up to 14 participants with FD will be enrolled to receive study intervention in 4 cohorts:

- Cohort 1: 3 Fabrazyme experienced female participants (body weight \geq 30 kg).
- Cohort 2: 3 Fabrazyme experienced non-classic male participants (body weight ≥30 kg).
- Cohort 3: 4 Fabrazyme experienced classic male participants (body weight ≥30 kg).
- Cohort 4: 4 Fabrazyme experienced participants (body weight <30 kg).

Classic FD is defined by α GAL level in dried blood spot or leukocyte below 3% of normal value and all others are considered as non-classic disease.

The study schema is presented in Section 1.2. Screening will be performed up to 4 weeks prior to the first dose of study intervention. All 4 cohorts of this study will be enrolled simultaneously. Enrolled participants will receive treatment for up to 16 weeks (up to 9 infusions) and have an End-of-Study Visit 28 weeks after the start of the treatment. Participants will undergo visits and study procedures as shown in Schedule of Activities (SoA) presented in Section 1.3.

All participants will receive Fabrazyme infusions at dose of 1 mg/kg at the study site. The participants are not required to stay at the site after completion of the infusion, unless the Investigator considers it medically necessary. The infusion duration will shorten, and the infusion rate will rise with each successfully tolerated infusion (ie, an infusion completed within a duration not exceeding 120% of planned duration, without infusion associated reaction [IAR]), until reaches the minimum infusion duration of 20 minutes for participants in cohorts 1 to 3 (≥30 kg) and 30 minutes for participants in cohort 4 (<30 kg). Guidance for increasing the rate of infusion (and consequently decreasing the infusion duration) are presented in Section 6.2. When the participant successfully reaches the shortest infusion duration planned for the cohort which he/she belongs, he/she will be considered a treatment completer and will not receive any further infusion as part of the study, regardless of whether the treatment period reaches 16 weeks or not.

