3.1.1 Infusion Duration Guideline

All participants will receive Fabrazyme infusions at dose of 1 mg/kg of body weight every 2 weeks at the study site, for up to 16 weeks. The infusion duration will shorten, and the infusion rate will rise with each successfully tolerated infusion, until they reach the minimum infusion duration of 20 minutes for participants in cohorts 1 to 3 (≥30 kg) and 30 minutes for participants in cohort 4 (<30 kg). When the participant successfully reaches the shortest infusion duration planned for the cohort which he/she belongs to, he/she will be considered a treatment completer and will not receive any further infusion as part of the study, regardless of whether the treatment period reaches 16 weeks or not.

Infusion duration tolerated by a participant is an infusion at which they successfully receive an infusion within an actual duration not exceeding 120% of planned duration without an IAR. If the participant receives several infusions at the same planned duration during the treatment period, the infusion duration will be considered tolerated if the last infusion received is without IAR and does not exceed 120% of planned duration.

The decrease in the infusion duration for participants in cohorts 1 to 3 (with \geq 30 kg body weight) will follow the flow diagram presented in Figure 2. The decrease in the infusion duration for participants in cohort 4 (with \leq 30 kg body weight) will follow the flow diagram presented in Figure 3.

Document: \\ieedc

 $vnasc01\BIOS data\Sanofi\Fabrazyme\IAB16602\Biostatistics\Documentation\SAP\SAP\Sanofi\Final$

Version\lps17726-16-1-9-sap.docx

Author: Version Number: Final V1.0

Version Date: 22Oct2024

[figure not shown]
Template No.: CS_TP_BS016 Revision 7 Reference: CS_WI_BS005

Effective Date: 01Nov2021

Page 20 of 65

Figure 2: Guideline for Decreasing Infusion Duration for Participants ≥30 kg

Abbreviations: IAR = infusion associated reaction.

Note: IARs occurring during a single infusion are counted as one IAR. Only when an IAR occurs in relation to a separate infusion it will be considered as a second IAR.

Note: When a second IAR occurs, the participant will discontinue study intervention and the previous highest rate tolerated by the participant will be considered as the maximum tolerated rate for this participant.

Document: \\ieedc

Author:

vnasc01\BIOSdata\Sanofi\Fabrazyme\IAB16602\Biostatistics\Documentation\SAP\SAP\Sanofi\Final

Version\lps17726-16-1-9-sap.docx

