7.3 MISSING DATA

7.3.1 PRIMARY, SECONDARY AND EXPLORATORY ENDPOINTS

7.3.1.1 PRIMARY ENDPOINTS

7.3.1.1.1 ACTUAL INFUSION DURATION

If actual infusion duration, see Section 15.1.2, cannot be calculated due to a partial date and/or time combination of any terms in the derivation, including interruption times then the actual duration will be set to the planned duration. Missing or partial dates for infusion start/stop and interruption times will not be imputed.

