15.1.1.2 PERCENT REDUCTION OF INFUSION DURATION FROM PRE-STUDY AVERAGE OF RECENT 3 INFUSIONS

Percent reduction is with respect to the shortest tolerated infusion for the participant.

The pre-study infusion duration is derived as the average of the duration of 3 most recent

Document: \\ieedc-

 $vnasc01\\BIOS data\\Sanofi\\Fabrazyme\\IAB16602\\Biostatistics\\Documentation\\SAP\\SAP\\Sanofi\\Finally and the properties of t$

Version\lps17726-16-1-9-sap.docx

Author: Version Number: Final V1.0

Version Date: 22Oct2024

Template No.: CS_TP_BS016 Revision 7 Reference: CS_WI_BS005

Effective Date: 01Nov2021

PROTOCOL LPS17726

Analysis Plan Template

Page 44 of 65

infusions the participant received prior to participating to this study. Data for pre-study infusion durations are captured on the Pre-Study Fabrazyme Treatment eCRF page.

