15.1.2 DERIVATIONS

- Infusion Interruption Duration (minutes) = (Interruption Stop Time Interruption Start Time)
- Actual infusion duration (minutes) = (Infusion Stop Time Infusion Start Time) –
 Infusion Interruption Duration (minutes)
- Average of pre-study infusion duration (minutes) = sum of all pre-study infusion duration (minutes) / number of pre-study infusions
- Percentage reduction of infusion duration (%) =100*[(Average of pre-study infusion duration (minutes) Actual shortest infusion duration tolerated (minutes)] /Average of pre-study infusion duration (minutes)
- Percentage change of infusion duration (%) =100*[Actual shortest infusion duration tolerated (minutes) Average of pre-study infusion duration (minutes)] /Average of pre-study infusion duration (minutes)

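### When a partial time blocks the calculation, the SAP sets actual infusion duration to planned duration, so the 120% condition for a tolerated infusion cannot fail

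*SAP*

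**What the plan says.** SAP 15.1.1.1 calls an infusion tolerated when it is "completed within an actual duration (excluding any interruptions) not exceeding 120% of planned duration, without IAR". SAP 15.1.2 derives actual duration as infusion stop minus infusion start, less the time interrupted. SAP 3.1.1 states the same test in terms of actual duration: "they successfully receive an infusion within an actual duration not exceeding 120% of planned duration without an IAR".

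SAP 7.3.1.1.1 covers incomplete records. If a partial date or time blocks the calculation through "any terms in the derivation, including interruption times then the actual duration will be set to the planned duration". The trigger is any term, so one partial interruption time is enough even when infusion start and stop are fully recorded.

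The other conditions in SAP 15.1.1.1 are untouched. The whole planned amount must be delivered, the eCRF must show the infusion as unchanged or interrupted, and there must be no IAR. An interrupted infusion must also have been restarted, which is read from whether "the stop time of study drug infusion is later than the stop time of infusion interrupted".

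The result feeds both primary endpoints (shortest tolerated duration and % reduction) and the secondary responder endpoints. Neither document plans a sensitivity analysis of the rule. SAP section 4 mentions exploratory analyses at the sponsor's discretion but names none.

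**The concern.** The 120% limit separates an infusion that ran close to plan from one that did not. The fallback removes that check exactly where the duration is unverified, and enters the planned value as though it had been observed. Where start and stop are known, it also discards usable information: stop minus start is an upper bound on net running time.

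This differs from how the SAP treats other undeterminable values. Compliance with a missing dose becomes not assessable (14.1), a lyso-GL3 sample that cannot be placed before the infusion is missing (15.3.1.1.1), and a treatment-emergent event with no recorded relationship is counted as related (7.3.2.2.2).

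A second gap follows from the first. If the interruption stop time is the partial one, the restart check cannot be evaluated as written, and the SAP does not say what happens then.

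At stake is whether some participants are credited with their 20- or 30-minute target on an infusion whose duration was never established. In a small, single-arm, descriptive study, such derivation rules carry much of the result.

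**Working it through.** The plan states no figure for this rule to reproduce; sample size rests on feasibility (SAP 17). The cohorts add up as stated: 3 + 3 + 4 + 4 = 14.

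**Inputs from the documents.** Limit 120% of planned duration (SAP 15.1.1.1). Shortest planned durations 20 minutes (≥30 kg) and 30 minutes (<30 kg) (Protocol 4.1). Up to 14 participants, ten of them ≥30 kg and four <30 kg.

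**Step 1: the test with complete times.** Tolerated requires (stop − start − interruption) / planned ≤ 1.20. The limits are 1.2 × 20 = 24 minutes and 1.2 × 30 = 36 minutes.

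**Step 2: the test after the fallback.** Planned / planned = 100%, which is always below 120%.

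**Step 3: an example (assumed times).** Plan 20 minutes, start and stop 50 minutes apart, interruption stop time partial.
- If the pause was really 30 minutes, net time is 50 − 30 = 20 minutes, 100% of plan: a pass.
- If it was really 10 minutes, net time is 50 − 10 = 40 minutes, 200% of plan: a fail on the SAP's own net-time rule.

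The record cannot tell these apart. The fallback gives 20 minutes and a pass on duration in both.

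**Step 4: one participant.** If a 20-minute infusion is reclassified and the preceding tolerated step was 30 to 60 minutes (assumed, because the step figures are not shown), % reduction changes as follows:

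| Assumed pre-study average (min) | At 20 min | At 30 to 60 min |
|---|---|---|
| 90 | 77.8% | 66.7% to 33.3% |
| 120 | 83.3% | 75.0% to 50.0% |
| 180 | 88.9% | 83.3% to 66.7% |

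Formula: 100 × (average − duration) / average; for example 100 × (120 − 20) / 120 = 83.3%.

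**Step 5: responder endpoints.** 1/14 = 7.1 points per reclassified participant: 100%, 92.9%, 85.7% for none, one and two, starting from 14 of 14.

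**Step 6: pooled medians.** Assume all reach target: ten at 20 minutes and four at 30, with actual equal to planned. The median is the mean of the 7th and 8th ordered values. Let k of the ten move to 30 to 60 minutes. For % reduction, further assume pre-study averages of 120 minutes (the ten) and 90 minutes (the four), so the four sit at 100 × (90 − 30) / 90 = 66.7%.

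| k | Median shortest duration | Median % reduction |
|---|---|---|
| 0 to 2 | 20 min | 83.3% |
| 3 | (20 + 30)/2 = 25 min | 79.2% to 75.0% |
| 4 | (30 + 30)/2 = 30 min | 75.0% to 66.7% |

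For k = 3 the ends are (83.3 + 75.0)/2 = 79.2% with a 30-minute step and (83.3 + 66.7)/2 = 75.0% with a 60-minute step.

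**The case against.** The fallback may hardly ever be used. Infusions are supervised, and Protocol 6.5 requires start and stop times to be recorded. Only the duration condition is waived: any IAR, broadly defined in Protocol 8.5.6, still fails the infusion, as does incomplete delivery. Set-to-plan does not always flatter either. If the true net time was shorter than planned, it lengthens the recorded duration and lowers the % reduction. If a step is repeated, the last infusion at that duration decides, so a later well-documented one supersedes the doubtful one. A participant who loses only the final step can still meet the under-90-minute endpoint on an earlier infusion. Listings and waterfall plots of individual values are planned (SAP 15.1.4), and the output templates, which were not available for this review, might flag the affected infusions.

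These points limit the size and stand as such. They do not restore the 120% check. Protection by a repeated step is also weakest at the target, because treatment ends once the site judges that step successful (Protocol 4.5).

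A reader might go further and infer that leaving pauses out of the 120% test is itself an error, or that the SAP contradicts itself or the protocol. The documents do not support this. SAP 15.1.2 defines actual duration net of interruptions, so SAP 3.1.1, which uses that term, agrees with 15.1.1.1. Net time also suits an endpoint that SAP 15.1.1.1 equates with the highest infusion rate. The protocol speaks of "an infusion completed within a duration not exceeding 120% of planned duration" and is silent on pauses.

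**Conclusion.** The point holds for the fallback rule. For any infusion with a blocking partial time, the 120% condition is met by construction, even against recorded times that leave it in doubt, and restart has no decision rule when the interruption stop time is partial.

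The size is conditional. At full enrolment each reclassified participant moves an affected responder endpoint by 7.1 points. The pooled medians need at least three such participants before they move, given ten at 20 minutes, four at 30, and the assumed pre-study averages and preceding steps. The documents do not say how often times are partial, so the realised effect may be nil.

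It would be wrong to conclude that such infusions are declared tolerated outright, or that the results are known to be biased upwards: the remaining conditions apply, and the direction for the recorded duration can go either way. Nor is a clock-time analysis needed to settle the point; it is optional.

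**What to change.** Amend SAP 7.3.1.1.1 and 15.1.1.1 before database lock so that an imputed duration cannot satisfy the 120% test by itself.

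1. Where start and stop are known and only an interruption time is partial, count the duration condition as met if stop minus start is at most 120% of planned. Otherwise class it as not established.
2. Where start or stop is itself partial, also class it as not established.
3. Treat all not-established infusions alike, so that a better-documented infusion is not handled more harshly than a poorly documented one. Either count them as not tolerated in the main analysis, or keep set-to-plan there and pre-specify a sensitivity analysis of both primary endpoints and the responder endpoints that counts them as not tolerated.
4. State how restart is decided when the interruption stop time is partial, for example by taking recorded full delivery as evidence of restart.
5. Flag infusions that used set-to-plan in the listings and report their number.

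The cost is SAP wording, a flag and a count, plus one set of sensitivity summaries if the second option in item 3 is chosen. The inputs are times already in the derivation. The downside is that a few truly tolerated infusions may be counted as not tolerated. With net time exactly on plan, item 1 fails once the pauses exceed 24 − 20 = 4 minutes or 36 − 30 = 6 minutes. This changes the analysis derivation only, not the sites' rule for moving between infusion steps.
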